13	LogMAR (ETDRS) Visual Acuity	
Using the Sekonic light meter with ISO1 setting of 125 under high illumination (>7.3 EV) and high chart luminance (9.9-10.7 EV) record the distance ETDRS high contrast:
 
 1. OD: Chart HC1 2. OS: Chart HC2 3. OU: Chart HC3 	
14	Lens Fit Assessment:	
Subjective Assessment of the Lens Fit. If the fit is graded as unacceptable based on the criteria below, then the subject is discontinued from the study and will not be replaced.
 
 1. Limbal exposure in any gaze 2. Edge lift 3. Insufficient and/or excessive movement in all three movement categories 	
15	Lens Deposits	Record the front and back surface deposits of the lenses.	
16	Lens Wettability	Record the white light lens wettability of both lenses.	
17	Lens Damage	Lens damage (draw in source document and describe). Replace lens if damaged and complete the Product Quality Complaint form and save lens in vial with Optifree PureMoist or saline.	
18	Lens Removal & Storage	
The worn lenses will be removed, stored in the following manner, and returned to the Sponsor:
 
 1. OD and OS lens stored wet in a labeled vial with Opti-Free PureMoist. The lenses should not be rubbed. 2. The lenses will be stored and shipped cold (refrigerated or frozen). 	
19	Slit Lamp Findings	
Slit Lamp Classification Scale [REDACTED] will be used to grade the findings. Record only whole numbers.
 
Note: Subject must be free of any FDA grade 3 or greater slit lamp findings with no active ocular infection/inflammation.
	
20	Eye Rinse	The study coordinator, investigator, or technician will rinse the subject's eyes thoroughly with saline.	

VISIT 5: Lens Assignment #4**(24-32 days after Visit 4)****The following information will be collected:**

Steps		Details	
1	Lens Information	The same lens type and power of the previous study lens must be chosen. The investigator or subject will place the lenses on. Quickly check for any lens damage and replace if necessary.	
2	Lens Damage	Lens damage (draw in source document and describe). Replace lens if damaged and complete the [REDACTED] form and save lens in vial with saline.	

VISIT 5: FITTING #4**(24-32 days after Visit 4)****The following information will be collected:**

Steps		Details	
1	Time Interval	Please wait at least 5 minutes before continuing.	
2	Spherical Over-refraction	Perform a spherical over-refraction OD and OS using any acceptable means (i.e., phoropter, trial lenses, flipper bars) in normal room illumination and record the resultant distance Snellen visual acuity OD and OS. A 0.00 D spherical over-refraction must be achieved to continue.	
3	Lens Modification Criteria	The lens power will be modified if the over-refraction is ± 0.25 D or more in either eye. One modification attempt is allowed.	

VISIT 5: TRIAL FITTING LENS MODIFICATION**(If needed, one modification is allowed)****The following information will be collected:**

Steps		Details	
1	Lens Information	The lens power will be chosen based on the over-refraction results from the first trial lenses.	
2	Lens Damage	Lens damage (draw in source document and describe). Replace lens if damaged and complete the [REDACTED] form and save lens in vial with saline.	
3	Time Interval	Please wait at least 5 minutes before continuing.	

VISIT 5: TRIAL FITTING LENS MODIFICATION		(If needed, one modification is allowed)	
The following information will be collected:			
Steps	Details		
4	Spherical Over-refraction	Perform a spherical over-refraction OD and OS using any acceptable means (i.e., phoropter, trial lenses, flipper bars) in normal room illumination and record the resultant distance Snellen visual acuity OD and OS. If a 0.00 D spherical over-refraction OD and OS is not demonstrated, the subject is terminated from the study; complete the Final Evaluation.	

VISIT 5: FITTING #4, CONTINUED		(24-32 days after Visit 4)
The following information will be collected:		
Steps	Details	
1	Subject-reported Ocular Symptoms	The subject will respond to a Symptoms Questionnaire.
2	Dispensing Questionnaire	Subjects will respond to the Dispensing Questionnaire for initial comfort and vision (ID: ISOC0001, ISOV0001)
3	LogMAR (ETDRS) Visual Acuity	Using the Sekonic light meter with ISO1 setting of 125 under high illumination (>7.3 EV) and high chart luminance (9.9-10.7 EV) record the distance ETDRS high contrast: 1. OD: Chart HC1 2. OS: Chart HC2 3. OU: Chart HC3
4	Lens Fit Assessment:	The fit of the lens is judged by the investigator as pass or fail based on the criteria below. If the fit of the lens is judged as a failure, the subject is terminated from the study. To be judged as a failure, the lens must display one or more of the following: 1. Limbal exposure in any gaze 2. Edge lift 3. Insufficient and/or excessive movement in all three movement categories
5	Lens Deposits	Record the front and back surface deposits of the lenses.
6	Lens Wettability	Record the white light lens wettability of both lenses.

VISIT 5: FITTING #4, CONTINUED**(24-32 days after Visit 4)****The following information will be collected:**

Steps		Details	
7	Continuance	
For the subject to continue in the study, they must meet all three of the following criteria:
 
1. Visual acuity is 0.17 logMAR (20/30) or better OD and OS.2. The lens fit is acceptable OD and OS3. Investigator approval. If the investigator does not approve the dispensing of the first study lens, then the study is terminated for that subject.	

VISIT 5: DISPENSING #4**(24-32 days after Visit 4)****The following information will be collected:**

Steps		Details	
1	Dispense	
The lenses will be dispensed for 24-32 days.
 
1. The subjects should wear their lenses similar to the inclusion criteria: \geq 6 hours per day, \geq 5 days per week.2. The lenses will be worn as daily wear only.3. All subjects will be provided Opti-Free PureMoist to be used in a rub regime.4. Preservative-free rewetting drops are permitted if needed.5. The lenses must be stored in the supplied case out of direct sunlight. 
Note 1: In the event a lens is lost or damaged, the subject will return to the investigator site for replacement (extra lenses cannot be given at the dispensing visit).
 
Note 2: The subject's habitual contact lenses cannot be worn until during Visit 6 when they are placed back into their habitual lenses.
 
Note 3: The subject will leave with the pair of study lenses that they have on their eyes, and with one additional pair to replace in approximately 14 days. The worn lenses will both be stored dry at room temperature at home in a labeled container and brought with them to visit 6.
 
Note 4: The subjects need to be reminded to bring their habitual contact lenses with them to their next visit.
	
2	Follow-up Visit Scheduling	An appointment for the next visit should be made for approximately 28 days (range 24-32 days) after Visit 5. Subjects should be advised to wear the study lenses at least 6 hours a day, and a minimum of 5 days per week. The study lenses must be worn into the Follow-up Visit.	

VISIT 6: 84-DAY FOLLOW-UP		(Follow-up #5, 24-32 days after Visit 5)
The following information will be collected:		
Steps	Details	
1	Concomitant Medications and Medical History Review	Record the concomitant medications and review the subject's medical history, specifically noting any changes from baseline.
2	Wearing Time	Record the average wearing time and comfortable wearing time.
3	Compliance	Confirm compliance with the prescribed wear schedule, including adherence to the rub regime.
4	Use of Lens Rewetting Drops	The subjects will record the approximate daily use of lens rewetting drops (i.e., how many times per day on average).
5	Subject-reported Ocular Symptoms	The subject will respond to a Symptoms Questionnaire.
6	Glare Questionnaire	The subject will respond to the Eyestrain Caused by Glare Questionnaire in regards to their study lenses.
7	Project-Specific Questionnaire	The subject will respond to the Project-Specific Questionnaire
8	CLUE Follow-up Questionnaire	The subject will respond to the CLUE Follow-up Questionnaire
9	Patient Reported Outcomes	Subjects will respond to the following individual questions. 1. Subjective Comfort (Item ID: ISOC0001) 2. Subjective Vision (Item ID: ISOV0001) 3. Subjective Handling (Item ID: ISOH0001)
10	GSI Product Performance Questionnaire	Subjects will respond to the GSI Product Performance Questionnaire.
11	Entrance Visual Acuity	Record the distance visual acuity with the contact lenses (OD, OS, and OU) to the nearest letter. Smaller lines must be shown until the subject incorrectly identifies at least 50% of the letters.
12	Spherical Over-refraction	Perform a spherical over-refraction OD and OS using any acceptable means (i.e., phoropter, trial lenses, flipper bars) in normal room illumination and record the resultant distance Snellen visual acuity OD and OS.

The following information will be collected:

Steps	Details	
13	LogMAR (ETDRS) Visual Acuity	Using the Sekonic light meter with ISO1 setting of 125 under high illumination (>7.3 EV) and high chart luminance (9.9-10.7 EV) record the distance ETDRS high contrast: 1. OD: Chart HC1 2. OS: Chart HC2 3. OU: Chart HC3
14	Lens Fit Assessment:	Subjective Assessment of the Lens Fit. If the fit is graded as unacceptable based on the criteria below, then the subject is discontinued from the study and will not be replaced. 1. Limbal exposure in any gaze 2. Edge lift 3. Insufficient and/or excessive movement in all three movement categories
15	Lens Deposits	Record the front and back surface deposits of the lenses.
16	Lens Wettability	Record the white light lens wettability of both lenses.
17	Lens Damage	Lens damage (draw in source document and describe). Replace lens if damaged and complete the Product Quality Complaint form and save lens in vial with Optifree PureMoist or saline.
18	Lens Removal & Storage	The worn lenses will be removed, stored in the following manner, and returned to the Sponsor: 1. OD and OS lens stored wet in a labeled vial with Opti-Free PureMoist. The lenses should not be rubbed. 2. The lenses will be stored and shipped cold (refrigerated or frozen).
19	End of study treatment time	The supplied test and control lenses will no longer be in use.
20	Slit Lamp Findings	Slit Lamp Classification Scale [REDACTED] will be used to grade the findings. Record only whole numbers. Note: Subject must be free of any FDA grade 3 or greater slit lamp findings with no active ocular infection/inflammation.
21	Eye Rinse	The study coordinator, investigator, or technician will rinse the subject's eyes thoroughly with saline.

VISIT 6: 84-DAY FOLLOW-UP

(Follow-up #5, 24-32 days after Visit 5)

The following information will be collected:

Steps	Details	

VISIT 6: HABITUAL LENS ASSIGNMENT #1

(24-32 days after Visit 5)

The following information will be collected:

Steps	Details	
1	Lens Information	The subject or investigator will place the subject's habitual lenses on both eyes.

VISIT 6: HABITUAL LENS FITTING #1

(24-32 days after Visit 5)

The following information will be collected:

Steps	Details	
1	Time Interval	Please wait at least 5 minutes before continuing.
2	Spherical Over-refraction	Perform a spherical over-refraction OD and OS using any acceptable means (i.e., phoropter, trial lenses, flipper bars) in normal room illumination and record the resultant distance Snellen visual acuity OD and OS.
3	Subject-reported Ocular Symptoms	The subject will respond to a Symptoms Questionnaire.
4	Dispensing Questionnaire	Subjects will respond to the Dispensing Questionnaire for initial comfort and vision (ID: ISOC0001, ISOV0001)
5	LogMAR (ETDRS) Visual Acuity	Using the Sekonic light meter with ISO1 setting of 125 under high illumination (>7.3 EV) and high chart luminance (9.9-10.7 EV) record the distance ETDRS high contrast: 1. OD: Chart HC1 2. OS: Chart HC2 3. OU: Chart HC3

VISIT 6: HABITUAL LENS FITTING #1**(24-32 days after Visit 5)****The following information will be collected:**

Steps		Details	
6	Lens Fit Assessment:	
The fit of the lens is judged by the investigator as pass or fail based on the criteria below. If the fit of the lens is judged as a failure, the subject is terminated from the study. To be judged as a failure, the lens must display one or more of the following:
 
 1. Limbal exposure in any gaze 2. Edge lift 3. Insufficient and/or excessive movement in all three movement categories 	█ █
7	Lens Deposits	Record the front and back surface deposits of the lenses.	█
8	Lens Wettability	Record the white light lens wettability of both lenses.	█

VISIT 6: HABITUAL LENS RELEASE #1**(24-32 days after Visit 5)****The following information will be collected:**

Steps		Details	
1	Habitual Lens Release	
The subject's habitual lenses will be worn for 6-8 days.
 
 1. The subjects should wear their lenses similar to the inclusion criteria: ≥ 6 hours per day, ≥ 5 days per week. 2. The lenses will be worn as daily wear only. 3. All subjects will be provided Opti-Free PureMoist to be used in a rub regime. 4. Preservative-free rewetting drops are permitted if needed. 
Note: Daily disposable wearers do not need to adhere to the Optifree PureMoist solution and rub regime.
	█
2	Follow-up Visit Scheduling	An appointment for the next visit should be made for approximately 7 days (range 6-8 days) after Visit 6. Subjects should be advised to wear their habitual lenses at least 6 hours a day, and a minimum of 5 days per week. Their habitual lenses must be worn into the Follow-up Visit.	

VISIT 7: 7-DAY FOLLOW-UP HABITUAL LENS

(Follow-up #1, 6-8 days after Visit 6)

The following information will be collected:

Steps		Details	
1	Concomitant Medications and Medical History Review	Record the concomitant medications and review the subject's medical history, specifically noting any changes from baseline.	
2	Wearing Time	Record the average wearing time and comfortable wearing time.	
3	Compliance	Confirm compliance with the prescribed wear schedule, including adherence to the rub regime.	
4	Use of Lens Rewetting Drops	The subjects will record the approximate daily use of lens rewetting drops (i.e., how many times per day on average).	
5	Subject-reported Ocular Symptoms	The subject will respond to a Symptoms Questionnaire.	
6	Glare Questionnaire	The subject will respond to the Eyestrain Caused by Glare Questionnaire in regards to their habitual lenses.	
7	Project-Specific Questionnaire	The subject will respond to the Project-Specific Questionnaire	
8	CLUE Follow-up Questionnaire	The subject will respond to the CLUE Follow-up Questionnaire	
9	Patient Reported Outcomes	Subjects will respond to the following individual questions. 1. Subjective Comfort (Item ID: ISOC0001) 2. Subjective Vision (Item ID: ISOV0001) 3. Subjective Handling (Item ID: ISOH0001)	
10	Lens Preferences	Subjects will respond to preference questions relating back to their habitual lenses.	
11	GSI Product Performance Questionnaire	Subjects will respond to the GSI Product Performance Questionnaire.	
12	Entrance Visual Acuity	Record the distance visual acuity with the habitual contact lenses (OD, OS, and OU) to the nearest letter. Smaller lines must be shown until the subject incorrectly identifies at least 50% of the letters.	

The following information will be collected:

Steps		Details	
13	Spherical Over-refraction	Perform a spherical over-refraction OD and OS using any acceptable means (i.e., phoropter, trial lenses, flipper bars) in normal room illumination and record the resultant distance Snellen visual acuity OD and OS.	
14	Lens Fit Assessment:	Subjective Assessment of the Lens Fit. If the fit is graded as unacceptable based on the criteria below, then the subject is discontinued from the study and will not be replaced. 1. Limbal exposure in any gaze 2. Edge lift 3. Insufficient and/or excessive movement in all three movement categories	
15	Lens Deposits	Record the front and back surface deposits of the lenses.	
16	Lens Wettability	Record the white light lens wettability of both lenses.	
17	Temporary Lens Removal & Storage	The lenses will be removed and temporarily stored in suitable lens case with Opti-Free PureMoist or saline. The lenses will be reinserted in step 20.	
18	Slit Lamp Findings	Slit Lamp Classification Scale [REDACTED] will be used to grade the findings. Record only whole numbers. Note: Subject must be free of any FDA grade 3 or greater slit lamp findings with no active ocular infection/inflammation.	
19	Eye Rinse	The study coordinator, investigator, or technician will rinse the subject's eyes thoroughly with saline.	
20	Lens Re-Insertion	The same lenses removed in step 17 will be placed back on the eyes and worn for an additional 6-8 days.	
21	Exit Visual Acuity	Record the distance Snellen visual acuity with their habitual lenses (OD, OS, and OU) to the nearest letter. Smaller lines must be shown until the subject incorrectly identifies at least 50% of the letters.	
22	Follow-up Visit Scheduling	An appointment for the next visit should be made for approximately 7 days (range 6-8 days) after Visit 7. Subjects should be advised to wear their habitual lenses at least 6 hours a day, and a minimum of 5 days per week. The habitual lenses must be worn into the Follow-up Visit.	

VISIT 8: 14-DAY FOLLOW-UP HABITUAL LENS		(Follow-up #2, 6-8 days after Visit 7)
The following information will be collected:		
Steps	Details	
1	Concomitant Medications and Medical History Review	Record the concomitant medications and review the subject's medical history, specifically noting any changes from baseline.
2	Wearing Time	Record the average wearing time and comfortable wearing time.
3	Compliance	Confirm compliance with the prescribed wear schedule, including adherence to the rub regime.
4	Use of Lens Rewetting Drops	The subjects will record the approximate daily use of lens rewetting drops (i.e., how many times per day on average).
5	Subject-reported Ocular Symptoms	The subject will respond to a Symptoms Questionnaire.
6	Glare Questionnaire	The subject will respond to the Eyestrain Caused by Glare Questionnaire in regards to their habitual lenses.
7	Project-Specific Questionnaire	The subject will respond to the Project-Specific Questionnaire
8	CLUE Follow-up Questionnaire	The subject will respond to the CLUE Follow-up Questionnaire
9	Patient Reported Outcomes	Subjects will respond to the following individual questions. 1. Subjective Comfort (Item ID: ISOC0001) 2. Subjective Vision (Item ID: ISOV0001) 3. Subjective Handling (Item ID: ISOH0001)
10	GSI Product Performance Questionnaire	Subjects will respond to the GSI Product Performance Questionnaire.
11	Entrance Visual Acuity	Record the distance visual acuity with the habitual contact lenses (OD, OS, and OU) to the nearest letter. Smaller lines must be shown until the subject incorrectly identifies at least 50% of the letters.
12	Spherical Over-refraction	Perform a spherical over-refraction OD and OS using any acceptable means (i.e., phoropter, trial lenses, flipper bars) in normal room illumination and record the resultant distance Snellen visual acuity OD and OS.

VISIT 8: 14-DAY FOLLOW-UP HABITUAL LENS

(Follow-up #2, 6-8 days after Visit 7)

The following information will be collected:

Steps		Details	
13	Lens Fit Assessment:	
Subjective Assessment of the Lens Fit. If the fit is graded as unacceptable based on the criteria below, then the subject is discontinued from the study and will not be replaced.
 
 1. Limbal exposure in any gaze 2. Edge lift 3. Insufficient and/or excessive movement in all three movement categories 	
14	Lens Deposits	Record the front and back surface deposits of the lenses.	
15	Lens Wettability	Record the white light lens wettability of both lenses.	
16	Temporary Lens Removal & Storage	The lenses will be removed and temporarily stored in suitable lens case with Opti-Free PureMoist or saline until the completion of the visit.	
17	Slit Lamp Findings	
Slit Lamp Classification Scale [REDACTED] will be used to grade the findings. Record only whole numbers.
 
Note: Subject must be free of any FDA grade 3 or greater slit lamp findings with no active ocular infection/inflammation.
	
18	Eye Rinse	The study coordinator, investigator, or technician will rinse the subject's eyes thoroughly with saline.	

VISIT 8: FINAL EVALUATION

(Normally 6-8 days after Visit 7)

The final evaluation will ordinarily take place after Visit 8 is completed. It may also take place at any point the subject discontinues the study or is terminated from the study.

Step		Details	
1	Final Exam Form	Indicate if the subject completed the study successfully or not. If subject discontinued, indicate the reason.	
2	Keratometry	Record the keratometry readings OD and OS in diopters. This should be captured with the same instrument used at baseline.	
3	Best-corrected Distance Visual Acuity	Record the subject's best corrected distance visual acuity with refraction OD, OS, and OU.	

VISIT 8: FINAL EVALUATION

(Normally 6-8 days after Visit 7)

The final evaluation will ordinarily take place after Visit 8 is completed. It may also take place at any point the subject discontinues the study or is terminated from the study.

Step	Details	
4	Comments and Signature Record any additional information on the page provided and sign the paper copy if applicable.	

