4.4.2 OPTIONAL FLOWCHART

4.5 RANDOMIZATION AND MASKING

Subjects will be randomly assigned to either JJVCI Investigational Contact Lens (Test) or ACUVUE OASYS (Control) groups based on a computer-generated randomization schedule prepared before the study by the sponsor Biostatistician. The randomization will be stratified by study site and randomly permuted blocks of 4 assignments will be used to achieve 1:1 Test versus Control lens type ratio within each study site.

The study site must follow the randomization scheme provided and complete enrollment according to the randomization list and not pre-select or assign subjects. The randomized assignment of subjects will be performed at the first visit prior to the first fitting. The following must have occurred prior to randomization:

- Informed consent has been obtained
- Subject meets all the inclusion / exclusion criteria
- Subject history and baseline information has been collected

This is a partially subject masked study. The dynamic nature (variable shade) of the Test lens makes full masking impossible. However, the identity of the Control lenses will be masked to the subject by way of investigational foil. This will reduce the likelihood that habitual wearers of ACUVUE OASYS recognize the Control lens and increase the likelihood that questionnaires will be answered unbiasedly.

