7	Visual Acuity	Record the distance Snellen visual acuity with the habitual lenses (OD, OS, and OU) to the nearest letter. Smaller lines must be shown until the subject incorrectly identifies at least 50% of the letters.
8	Remove Habitual Lens	The subject's habitual lenses will be removed and stored in their own lens case. If they forgot to bring their lens case, one will be provided to them.
9	Slit Lamp Findings	FDA Slit Lamp Classification Scale (████) will be used to grade the findings and will be used to determine eligibility. Record only whole numbers. If any of these slit lamp findings are grade 2 or higher, the subject is ineligible to continue; complete the Final Evaluation.
10	Iris Color	The investigator will record the subject's iris color based on the scale provided (Appendix B).
11	Keratometry	Record the keratometry readings OD and OS in diopters. This can come from any appropriate instrument so long as the same instrument is used at the Final Evaluation.
12	Subjective Refraction	The investigator will complete a subjective refraction (sphere and cylinder) and record the resultant distance visual acuity OD, OS, and OU to the nearest letter. Best corrected Snellen distance visual acuity (BVA) must be 20/25+3 or better in each eye.
13	Eligibility at Baseline	All responses to Inclusion Criteria questions must be answered "yes," and all responses to Exclusion Criteria questions must be answered "no" for the subject to be considered eligible.
14	Eye Rinse	The study coordinator, investigator, or technician will rinse the subject's eyes thoroughly with saline.

VISIT 1: Lens Assignment #1		Day 0
The following information will be collected:		
Steps	Details	
1	Lens Information	The Lens Randomization Table will be used to determine which study lens is worn. The lens powers are based on the vertexed (12mm), spherical equivalent subjective refraction (Appendix A). The investigator or subject will place the lenses on. Quickly check for any lens damage and replace if necessary.

VISIT 1: Lens Assignment #1			Day 0
The following information will be collected:			
Steps	Details		
2	Lens Damage	Lens damage (draw in source document and describe). Replace lens if damaged and complete the Product Quality Complaint form and save lens in vial with saline.	

VISIT 1: FITTING #1			Day 0
The following information will be collected:			
Steps	Details		
1	Time Interval	Please wait at least 5 minutes before continuing.	

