% = nx100/N; SD = Standard Deviation

a SLF reported during an unscheduled visit were included in the following scheduled visit.

b The percent (%) of Any SLF Grade 2 is calculated using Total Unique Eyes as a denominator.

Primary Safety Endpoint (Slit Lamp Findings):

The power was estimated from the formula given by Diggle et al. (2002)² for clustered binary data for a pre-specified sample size of N=50 per arm:

$$Z_{\beta} = \frac{\left[\sqrt{\frac{N \cdot \{n(p_1 - p_2)^2\}}{1 + (n-1) \cdot \rho}} - Z_{\alpha} \sqrt{2\bar{p}\bar{q}} \right]}{\sqrt{(p_1 q_1 + p_2 q_2)}}$$

where p_1 : Response proportion in group 1 (Test), $q_1 = 1 - p_1$, p_2 : Response proportion in group 2 (Control), $q_2 = 1 - p_2$, $\bar{p} = (p_1 + p_2)/2$, $\bar{q} = 1 - \bar{p}$, n : number of observations per cluster(n was set to 10; 2 eyes x 5 time points), N is the number of subjects per arm and ρ is the common correlation across the n observations. The term z_{α} is the z score that correspond to the pre-specified type I error error α . The term z_{β} is the z score that corresponds to the estimated power $1 - \beta$ for pre-specified size effects.

There were no SLF of grade 3 or 4 reported in any of the three studies. Using previous research in the *literature*^{4,5}, the anticipated proportion of eyes with any SLF grade 3 and 4 is estimated to be less than or equal to 0.5% in both test and control arms.

Table 2: Power calculation for various effect sizes and correlations for SLF

Test Proportion	Control Proportion	Delta	Rho	Power
0.001	0.0510	.005	0.25	33%
0.001	0.0510	.005	0.50	58%
0.001	0.0510	.005	0.75	71%
0.0025	0.0525	.005	0.25	36%
0.0025	0.0525	.005	0.50	61%
0.0025	0.0525	.005	0.75	73%
0.005	0.0550	.005	0.25	40%
0.005	0.0550	.005	0.50	64%
0.005	0.0550	.005	0.75	75%
0.01	0.0600	.005	0.25	48%
0.01	0.0600	.005	0.50	69%
0.01	0.0600	.005	0.75	78%

Primary Efficacy Endpoint (Visual Acuity):

The power calculations were performed using Diggle's formula (*Diggle et al.*; 2002)² for clustered continuous data for a pre-specified sample size of N=50 per arm:

$$Z_{\beta} = \sqrt{0.5 * \left(\frac{N(n[\frac{\mu_1 - \mu_2}{\sigma^2}]^2)}{1 + (n-1)\rho} \right)} - Z_{\alpha}$$

Where σ^2 is the assumed common variance in the two groups, $\mu_1 - \mu_2$: the difference in means between the two groups (Test - Control), n : number of observations per cluster, N is the number of subjects per arm and ρ is the common correlation across the n observations.

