6.2.2. Analysis Methods

Slit Lamp Findings (SLF)

SLF responses will be categorized into a binary outcome as 0 if no Grade 3 or higher SLF or 1 if any Grade 3 or higher SLF. Events occurring during an unscheduled visit will be counted in the subsequent scheduled visit. For example, if a SLF grade 3 or higher occurs between Visit 1 and Visit 2, it will be counted in Visit 2. If there are multiple events at a given time point for one eye, it will be counted only once. The safety endpoint will be analyzed using a Generalized Estimating Equation (GEE) model (Zeger and Liang; 1986)² with a binomial distribution and logit link function. The regression model will include terms for lens group, time (1-, 2-, 4-, 8- and 12-week) and the lens group by time interaction (group*time). Appropriate working correlation matrix will be selected to take on consideration the correlation between measurements within each subject using Quasilikelihood Information Criterion (QIC). Working correlation structures to be considered will include independence (IND), exchangeable (Exch), autoregressive AR(1) and unstructured (UN). The covariance structure that returns the lowest QIC will be selected as the structure that best fit the data. If all model fails to converge, a reduced model will be considered by removing group*time and time from the model.

For unadjusted estimates the odds ratio of outcome 1 between the Test and the Control groups will be calculated with a 95% confidence interval to test for the difference between the Test and Control groups. For adjusted estimates the odds ratio of outcome 1 between the Test and the Control groups will be calculated with a simultaneous 99% confidence interval to test for the difference between the Test and Control groups.

If there are no sufficient SLF findings of Grade 3 or higher, analysis will be performed on any SLF grade 2 or higher SLF. Further analyses by subject, visit and/or slit lamp findings category will also be considered if necessary.

Ocular Symptoms, problems or complaints

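### The grade 2+ fallback model for slit lamp findings leaves out the Visit 1 grade (0 or 1), a baseline value already collected that may be prognostic; minor in an exploratory study

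*Protocol*

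**What the plan says.** Protocol 4.7.1, Visit 1 Baseline Information, step 9: the FDA slit lamp scale "will be used to grade the findings and will be used to determine eligibility. Record only whole numbers". The next sentence reads: "If any of these slit lamp findings are grade 2 or higher, the subject is ineligible to continue; complete the Final Evaluation". Exclusion criterion 6 (Protocol 4.3) sets the same limit.

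Protocol 4.5 lists what must precede randomization, including: "Subject history and baseline information has been collected".

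SAP 6.2.2, Slit Lamp Findings, specifies a logistic GEE for any grade 3 or higher finding: "The regression model will include terms for lens group, time (1-, 2-, 4-, 8- and 12-week) and the lens group by time interaction (group*time"). Protocol 9.1 gives the same terms. If no model converges, time and the interaction are dropped. The fallback is: "If there are no sufficient SLF findings of Grade 3 or higher, analysis will be performed on any SLF grade 2 or higher SLF". No baseline term appears in the main, reduced or fallback model.

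SAP 1.5 says of the historical data: "There were no SLF of grade 3 or 4 reported in any of the three studies". It adds that "the anticipated proportion of eyes with any SLF grade 3 and 4 is estimated to be less than or equal to 0.5" per cent, in both arms.

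**The concern.** The fallback is the slit lamp comparison likely to carry the primary safety conclusion. On that outcome every randomized eye starts as a non-event, but not at the same distance from the threshold: a grade 1 eye is one grade away, a grade 0 eye two. If that difference predicts later findings, leaving it out discards known variation between subjects.

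The hypothesis is that the lenses do not differ statistically on this endpoint (SAP 1.4.1). Low power therefore favours missing a real excess on the Test lens. With about 50 subjects per arm, the arms may also differ by chance in the share of grade 1 eyes. A baseline table would show this, but a covariate added after seeing it would be post hoc.

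**Working it through.** **1. The plan's own figures.** Two arms of 50 subjects with two eyes give 200 eyes. At 0.5%, the expected number of eyes with a grade 3+ finding is 200 × 0.005 = 1. Treating eyes as independent, the chance of none is 0.995^200 = 0.37. If 0.5% is read per eye-visit instead, 1,000 × 0.005 = 5 are expected. The fallback is therefore likely, although the SAP sets no numerical trigger.

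The SAP's power table for slit lamp findings (Table 2) concerns grade 3+, so there is no plan figure for the fallback. Nor does Table 2 serve as a benchmark. For its first row (0.001 v 0.0510, rho 0.25, N = 50, n = 10) the SAP's formula at one-sided 0.01 gives

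z = [√(500 × 0.05² / 3.25) − 2.326 × √(2 × 0.026 × 0.974)] / √(0.001 × 0.999 + 0.051 × 0.949) = 0.43,

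that is, power 67%. The printed 33% is the type II error. That is a separate matter and nothing below rests on it.

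**2. The grade 3+ model.** In simulation at 0.5% per eye-visit, 40% to 70% of trials had no event in an arm or in an entry-grade level, so the model could not be estimated. In the rest, rejection was below 1% with or without entry grade.

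**3. The grade 2+ fallback.** Inputs from the documents: 50 per arm, 2 eyes × 5 visits, two-sided 0.05. Everything else is assumed. Each simulated trial was analysed by logistic GEE (independence working correlation, robust SE clustered by subject) with and without entry grade.

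Set A: Test lower than Control; subject SD 1.2 and eye SD 0.8 on the logit scale; 4,000 trials per row. The 23% is the Control rate at week 2 in SAP Table 1; the 5% is assumed.

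| Control v Test | Grade 1 share | Entry-grade OR | Power without | Power with | Gain (points) |
|---|---|---|---|---|---|
| 23% v 13% | 20% | 1 | 75.3% | 75.4% | 0.1 |
| 23% v 13% | 20% | 2 | 74.8% | 75.7% | 0.9 |
| 23% v 13% | 20% | 5 | 68.4% | 74.3% | 5.9 |
| 23% v 14% | 20% | 10 | 60.5% | 73.7% | 13.2 |
| 23% v 13% | 40% | 2 | 73.7% | 75.5% | 1.8 |
| 23% v 13% | 40% | 5 | 66.4% | 73.4% | 7.0 |
| 23% v 14% | 40% | 10 | 58.9% | 70.9% | 12.0 |
| 5% v 1.8% | 40% | 2 | 62.7% | 63.8% | 1.1 |
| 5% v 1.8% | 40% | 5 | 58.4% | 60.7% | 2.3 |
| 5% v 1.9% | 40% | 10 | 53.0% | 57.3% | 4.3 |

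Set B: an excess on Test, the direction that matters for safety; subject SD 1. The entry-grade OR follows from the two Control risks, for example (0.25/0.75)/(0.04/0.96) = 8.0.

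| Control risk from grade 0 / grade 1 | Entry-grade OR | Grade 1 share | Lens OR | Power without | Power with | Gain (points) |
|---|---|---|---|---|---|---|
| 8% / 12% | 1.6 | 40% | 2.5 | 87.3% | 87.6% | 0.3 |
| 10% / 18% | 2.0 | 40% | 2.5 | 89.8% | 90.8% | 1.0 |
| 2% / 4% | 2.0 | 40% | 2.5 | 62.2% | 62.7% | 0.5 |
| 1.5% / 5% | 3.5 | 40% | 2.5 | 58% | 61% | 3 |
| 6% / 20% | 3.9 | 40% | 2.0 | 55% | 63% | 8 |
| 4% / 25% | 8.0 | 40% | 2.0 | 41% | 60% | 19 |
| 4% / 25% | 8.0 | 40% | 2.5 | 67% | 85% | 18 |
| 3% / 20% | 8.1 | 30% | 2.5 | 61% | 78% | 17 |
| 3% / 30% | 13.9 | 50% | 2.0 | 43% | 64% | 21 |

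With no lens effect, rejection was 5.7% without and 6.3% with the covariate (set A inputs: 23%, share 40%, entry-grade OR 5), and 6.2% for both (set B inputs: 4% / 25%, share 40%).

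**4. Chance imbalance.** If 40% of eyes enter at grade 1 and the two eyes correlate at 0.5, the SD of the difference between arms in that share is √(2 × 0.4 × 0.6 × 0.75 / 50) = 0.085. At risks of 4% and 25%, one SD shifts the grade 2+ rate by 0.085 × 21 ≈ 1.8 points. If grade is instead common to both eyes and 20% to 50% of subjects are at grade 1, the 95% range is ±1.96 × √(2 × 0.2 × 0.8 / 50) = ±16 points to ±1.96 × √(2 × 0.5 × 0.5 / 50) = ±20 points.

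**5. Limits.** The models compared overall lens effects without the SAP's lens-by-time term, and with a fixed working correlation where the SAP chooses one by QIC. The safety set may exceed 50 per arm.

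**The case against.** An unadjusted randomized comparison is valid, and the SAP's hypothesis is about the percentage of eyes with findings, a marginal quantity. Adjusting in a logit model changes the target to an odds ratio conditional on entry grade. The study is a feasibility study with exploratory hypotheses (SAP 1.4), baseline values will be summarized (Protocol 9.1), and SAP 6.2.2 leaves room for further slit lamp analyses. All of this stands, and it limits the priority.

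Four stronger readings are tempting, and the documents do not support them:

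- **That the grade 3+ model also loses power.** About one affected eye is expected, so there is no usable power to lose. Another term would only make estimation failure more likely.
- **That SAP Table 1 shows grades persisting.** Control neovascularization was 17.6% then 14.0%, and tarsal findings 10.7% then 9.0%. These are arm-level grade 2 rates pooled over three studies. They do not link eyes across visits and say nothing about grade 0 v 1 at entry. Test eyes in the same table had grade 2 findings in only 1.9% and 3.3%.
- **That entry grade is known to be a strong predictor.** The one-step v two-step argument makes this plausible, but no figure in the documents supports it. The gain can be nil.
- **That chance imbalance biases the result.** Under randomization it is noise, already reflected in the standard error. It does not inflate the type I error.

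Step 9 also does not say that each eye is graded separately, unlike neighbouring steps. This is inferred from the per-eye endpoint in SAP 6.2.1.

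**Conclusion.** The point holds for the grade 2+ fallback only. A baseline value on the same scale is recorded before randomization, can take only two values, and is not used in the model likely to be run. The gain from using it is about 0 to 2 points of power at an entry-grade odds ratio of 1 to 2. At odds ratios of about 4 to 14 it is roughly 3 to 20 points (individual scenarios 2.3 to 21). The false-positive rate is about 6% with or without it. These sizes depend on an assumed prevalence and prognostic strength of grade 1. The unadjusted analysis is not invalid or biased; it may be less precise than it need be. Minor priority in an exploratory feasibility study.

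**What to change.** In SAP 6.2.2, add that the grade 2+ fallback model includes the eye's highest Visit 1 slit lamp grade (0 v 1) as one fixed covariate, and that any by-category grade 2+ analysis uses the Visit 1 grade of that category. Report the unadjusted odds ratio beside the adjusted one, and label the adjusted one as conditional on entry grade. State that only the unadjusted result is given if an entry-grade level has no events. Leave the grade 3+ model unchanged. Confirm that the case report form holds the Visit 1 grade by eye and category.

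The cost is a short addition to the SAP and one degree of freedom. If the form holds the grade by eye, no new data are needed. The downside is a second odds ratio with a different target to explain.
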